6.5 Safety

From baseline, all blood draws and safety assessments must be performed prior to study treatment administration. Appropriate safety assessments (e.g., evaluation of AEs and SAEs) should be repeated after dosing with study treatment.

6.5.1 Physical examination

A complete physical examination will include the examination of general appearance, skin, neck (including thyroid), eyes, ears, nose, throat, lungs, heart, abdomen, back, lymph nodes, and extremities, and the vascular and neurological systems. If indicated based on medical history and/or symptoms, rectal, external genitalia, breast, and pelvic exams will be examined.

Information for all physical examinations must be included in the source documentation at the study site. Significant findings that are present prior to signing the informed consent must be included in the Medical History eCRF page. Significant findings made after the first administration of investigational drug which meet the definition of an AE must be recorded on the Adverse Event section of the eCRF.

6.5.2 Vital signs

Vital signs include blood pressure and pulse measurements. After the patient has been sitting for 5 minutes, with the back supported and both feet placed on the floor, systolic and diastolic blood pressures will be measured 3 times using an automated validated device, e.g., OMRON, with an appropriately sized cuff. The repeat sitting measurements will be made at 1-2 minute intervals and the mean of the 3 measurements will be used. If the available cuff sizes are not large enough for the patient's arm circumference, a sphygmomanometer with an appropriately sized cuff may be used.

If possible, assessments should be performed by the same study site staff member throughout the study.

Normal blood pressure will be defined as a systolic pressure of 90 to < 120 mm Hg, and a diastolic blood pressure of 60 to < 80 mm Hg under the measurement conditions outlined above. Notable blood pressure findings will be hypertension (systolic blood pressure of \geq 140 mm Hg and/or diastolic blood pressure of \geq 90 mm Hg) or hypotension (systolic blood pressure of < 90 mm Hg and/or a diastolic blood pressure of < 60 mm Hg). A blood pressure indicative of prehypertension (systolic blood pressure of 120 to < 140 mm Hg and/or diastolic blood pressure of 80 to < 90 mm Hg) will not be regarded as notable ([Chobanian et al 2003](#)).

A normal pulse rate will be defined as a rate of 60 to 100 beats per minute (bpm) under the measurement conditions outlined above. Notable pulse rate will be a rate below 60 bpm (bradycardia) or above 100 bpm (tachycardia).

Whether action needs to be taken to address notable vital signs will be decided by the investigator, taking into account the overall status of the patient. No specific action is foreseen as part of the study protocol.

6.5.3 Height and weight

Height in centimeters (cm) and body weight (to the nearest 0.1 kilogram (kg) in indoor clothing, but without shoes) will be measured.

6.5.4 Laboratory evaluations

A central laboratory will be used for the analysis of blood and urine collected (with the exception of pregnancy tests). Details on the collection, shipment of samples and reporting of results by the central laboratory are provided to investigators in the laboratory manual. For the identification of notable values, the laboratory manual should be consulted. Whether action needs to be taken to address notable laboratory values will be decided by the investigator taking into account the overall status of the patient. No specific action is foreseen as part of the study protocol.

For clinically notable thresholds please refer to [Appendix 1](#) or to the laboratory manual.

6.5.4.1 Hematology

Hemoglobin, hematocrit, red blood cell count, white blood cell count with differential (neutrophils including bands, lymphocytes, monocytes, eosinophils, basophils), and platelet count will be measured.

6.5.4.2 Clinical chemistry

Blood urea, creatinine, total bilirubin, alkaline phosphatase, international normalized ratio, sodium, potassium, chloride, calcium, phosphorous, total protein, albumin, uric acid, and lipid panel will be measured.

For a local analysis of urine, dipsticks will be provided by the central laboratory to the sites for the assessment. Sites should record the results in the source documentation and report these in the eCRF for each patient.

6.5.4.3 High-sensitivity C-reactive protein

This marker will be assessed at the visits when clinical chemistry is performed (see [Table 6-1](#), [Table 6-2](#), and [Table 6-3](#)).

6.5.5 Electrocardiogram

For the baseline visit an ECG must be recorded after 10 minutes rest in the supine position to ensure a stable baseline. The preferred sequence of cardiovascular data collection at baseline is ECG collection first, followed by vital signs, and blood sampling. The Fridericia QT correction formula (QTcF) should be used for clinical decisions.

Only clinically significant abnormalities should be reported in the eCRF Adverse Event page. If the ECG findings are clinically relevant and would prevent the patient from participating in the study (taking into account the patient's overall status and the medication profile), the patient should be recorded as a screen failure, should not be enrolled and should not receive treatment.

Single 12-lead ECGs will be collected. The original ECGs, appropriately signed, should be collected and archived at the study site.

Each ECG tracing must be labelled with study number, patient initials, patient number, date and time, and filed in the study site source documents. Clinically significant ECG findings at baseline must be discussed with the sponsor before administration of study treatment.

6.5.6 Pregnancy

A serum or urine β -hCG test will be performed in all pre-menopausal women as shown in [Table 6-1](#), [Table 6-2](#), and [Table 6-3](#).

All pre-menopausal women who are not sterile at screening will also have a urine pregnancy test performed locally. Any woman with a confirmed positive pregnancy test ($\text{hCG} > 5 \text{ mIU/mL}$) during screening will not be eligible for randomization.

Women of childbearing potential should use an effective method of contraception while on treatment, or longer if required by locally-approved prescribing information (e.g., 20 weeks after the last dose in the EU and countries where applicable for secukinumab). A positive urine pregnancy test during the Treatment Epoch of the study requires immediate interruption of study treatment until serum β -hCG is performed and found to be negative. If the serum β -hCG test is positive, study treatment must be definitively discontinued, as described in [Section 5.6.2](#).

If a β -hCG test is positive during the Follow-up Epoch, the patient will be discontinued from the study.

6.5.7 Appropriateness of safety measurements

The safety assessments selected in this study are reliable and standard measures for a biologic immunomodulatory agent in adult patients with psoriasis.

[figure not shown]
[figure not shown]
6.6 Other assessments

6.6.1 Clinical outcome assessments

6.6.1.1 Clinician-reported outcomes

6.6.1.1.1 Evaluation of psoriasis arthritis symptoms

Questions about signs and symptoms of psoriatic arthritis including pain, swelling and stiffness of the joints, neck, back, fingers, toes, and entheses will be addressed and captured in the eCRF.

6.6.2 Resource utilization

Not applicable.

6.6.3 Pharmacokinetics

Not applicable.

6.6.4 Immunological analysis of skin biopsies

This study includes an optional biopsy collection which requires a separate informed consent if the patient agrees to participate in the Mechanistic Sub-study.

Skin biopsies will be taken from patients in Arm A1b, Arm A2, Arm B1b, Arm C1, and Arm C2 to assess the total number of T_{reg} cells and subsets of these cells, especially those capable of producing IL-17A and IL-22 inflammatory mediators considered to be vital to maintain subclinical inflammation.

Punch biopsies from lesional or resolved skin (2 biopsies, 4 millimeters in diameter) and never-lesional skin (1 biopsy, 3 millimeters in diameter) will be taken according to the schedule shown in [Table 6-6](#). After collection, biopsies need to be transported on ice or dry ice within 24 hours to the laboratory (Karolinska Institute, Stockholm, Sweden) for further processing using a Novartis delegated service provider.

Table 6-6 Schedule for the collection of skin biopsies

Arm	Collection time				
	Baseline	Week 16	Week 52	Week 104	Week 208
A1b	X	X	X	X ^a	X ^a
A2	X	X	X	X	X ^a
B1b	X	X	X	X ^a	X ^a
C1	X	X	X		
C2	X	X	X	X	

a) Only patients eligible for the Follow-up Epoch will have biopsies taken at the marked time points

Laboratory manuals will be provided with detailed information on sample collection, handling, and shipment. The sample collection date and exact time must be entered on the Sample Collection eCRF page.

7 Safety monitoring

7.1 Adverse events

[figure not shown]
An AE is any untoward medical occurrence (e.g., any unfavorable and unintended sign [including abnormal laboratory findings], symptom or disease) in a patient or clinical investigation subject after providing written informed consent for participation in the study until the EOS visit. Therefore, an AE may or may not be temporally or causally associated with the use of a medicinal (investigational) product.

In addition, all reports of intentional misuse and abuse of the product are also considered an AE irrespective if a clinical event has occurred. The occurrence of AEs must be sought by non-directive questioning of the patient at each visit during the study. Adverse events also may be detected when they are volunteered by the patient during or between visits or through physical examination findings, laboratory test findings, or other assessments.

Abnormal laboratory values or test results constitute AEs only if they fulfill at least one of the following criteria:

- they induce clinical signs or symptoms
- they are considered clinically significant
- they require therapy

Clinically significant abnormal laboratory values or test results must be identified through a review of values outside of normal ranges/clinically notable ranges, significant changes from

baseline (randomization) or the previous visit, or values which are considered to be non-typical in patient with underlying disease. Investigators have the responsibility for managing the safety of individual patient and identifying AEs. Alert ranges for laboratory and other test abnormalities are included in [Appendix 1](#).

Adverse events must be recorded in the Adverse Event eCRF page under the signs, symptoms or diagnosis associated with them, accompanied by the following information:

- the severity grade:
 - mild: usually transient in nature and generally not interfering with normal activities
 - moderate: sufficiently discomforting to interfere with normal activities
 - severe: prevents normal activities
- its relationship to the study treatment
 - no relationship to study treatment or other investigational treatment or
 - relationship to study treatment or
 - relationship to other investigational treatment or
 - relationship to both study treatment and other investigational treatment or indistinguishable
- its duration (start and end dates) or if the event is ongoing an outcome of not recovered/not resolved must be reported
- whether it constitutes a SAE (see [Section 7.2](#) for definition of SAE) and which seriousness criteria have been met
- action taken regarding the investigational treatment

[figure not shown]
All AEs must be treated appropriately. Treatment may include one or more of the following:

- no action taken (e.g., further observation only)
- investigational treatment dosage increased/reduced
- investigational treatment interrupted/withdrawn
- concomitant medication or non-drug therapy given
- patient hospitalized/patient's hospitalization prolonged (see [Section 7.2](#) for definition of SAE)
- its outcome (not recovered/not resolved; recovered/resolved; recovering/resolving, recovered/resolved with sequelae; fatal; or unknown)

Once an AE is detected, it should be followed until its resolution or until it is judged to be permanent, and assessment must be made at each visit (or more frequently, if necessary) of any changes in severity, the suspected relationship to the study treatment, the interventions required to treat it, and the outcome.

Worsening of psoriasis in this study is evaluated via the use of PASI, IGA mod 2011 [REDACTED] assessments and is not expected to be captured as an AE in the eCRF. Exceptions include cases when a) a new type of psoriasis is diagnosed (e.g. guttate psoriasis), and b) the worsening of psoriasis is so severe that a qualitatively different status is reached.

Information about common side effects already known about the study treatment can be found in the Investigator Brochure. This information will be included in the patient informed consent

and should be discussed with the patient during the study as needed. Any new information regarding the safety profile of the medicinal product that is identified between Investigator Brochure's updates will be communicated as appropriate, for example, via an Investigator Notification or an Aggregate Safety Finding. New information might require an update to the informed consent and has then to be discussed with the patient.

The investigator should also instruct each patient to report any new AE (beyond the protocol observation period) that the patient, or the patient's personal physician, believes might reasonably be related to study treatment. This information should be recorded in the investigator's source documents; however, if the AE meets the criteria of an SAE, it must also be reported to Novartis.

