5.6 Study completion and discontinuation

5.6.1 Study completion and post-study treatment

A patient will be considered to have completed the study when he or she has completed the last visit planned in the protocol.

Patients who have been screened and have a screening visit recorded in the IRT system at the time that the planned enrolment number is met will be allowed to enter the study and be randomized if they are eligible.

The investigator must provide follow-up medical care for all patients who are prematurely withdrawn from the study, or must refer them for appropriate ongoing care.

For all patients a safety follow-up visit should be conducted (e.g., by telephone) 30 days after the last study visit or 12 weeks after the last dose of study treatment, whichever is later. The information to be collected at this follow-up visit includes concomitant medications, AEs, and survival status.

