5.6.6 Discontinuation during the Follow-up Epoch

During the Follow-up Epoch, patients must be discontinued from the study under the following circumstances:

- Patient wish
- Pregnancy (see [Section 6.5.6](#))
- Use of prohibited treatment
- Any other protocol deviation that results in a significant risk to the patient's safety

- Occurrence of relapse

6 Visit schedule and assessments

Table 6-1, Table 6-2, and Table 6-3 list all of the assessments and indicates with an “X” the visits when they will be performed. An “S” indicates that the data for that assessment are to be recorded in the source documents at the site.

[figure not shown]
Patients should be seen for all visits on the designated day or as closely as possible to the originally planned visit. Missed or rescheduled visits should not lead to automatic discontinuation and will be discussed on an individual basis. The investigator and the patient can also request an unscheduled visit whenever necessary, especially during the treatment-free Follow-up Epoch where a worsening of symptoms and quality of life could occur, the investigator should remind the patient of this option.

Patients who prematurely discontinue the study for any reason should be scheduled for an EOS visit as soon as possible, at which time all of the assessments listed for the final visit (EOS) will be performed before any new treatment is initiated. All dispensed investigational product should be reconciled and the AEs and concomitant medications reconciled on the CRF.

At a minimum, patients will be contacted for safety evaluations during the 30 days following the last study visit or following the last administration of study treatment (see Section 5.6.1). Attempts to contact the patient should be recorded in the source documentation.

Table 6-1 Assessment schedule: Screening Epoch and Treatment Epoch (all arms)

	SE	Treatment Epoch																	
Visit number	SC ^a	1							2		3			4				5 ^b	U
Time (weeks)		B	1	2	3	4	8	12	16	20	24	28	32	36	40	44	48	52	
Secukinumab administration at the site		X							X		X			X					
Secukinumab administration at home			X	X	X	X	X	X		X		X	X		X	X	X		
nb-UVB (Arm B1)		One or 2 cycles (of 12-week duration each)																	
Informed consent	X																		
Provide patient diary		S																	
Inclusion/exclusion criteria	X	X																	
Randomization		X																	
Demographics	X																		
Medical history	X	X																	
Vital signs	X	X							X		X			X				X	X

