Vital signs	X	X	X	X	X	X	X	X	X	X	X	X	X	X	X
Weight					X									X	
Physical examination		S			S				S					S	S
Laboratory ^b		X			X				X					X	X
PASI assessment	X	X	X	X	X	X	X	X	X	X	X	X	X	X	X
IGA mod 2011	X	X	X	X	X	X	X	X	X	X	X	X	X	X	
hs-CRP		X			X				X					X	
Urine β-hCG		X			X				X					X	
Skin biopsies					X									X	
Prior/concomitant medication									X						X
AEs/SAEs									X						X

a) Arm A2 from Week 105 on.

b) Laboratory evaluations will include hematology and clinical chemistry.

c) EOS is defined as the last visit for a patient independently of whether the discontinuation or completion is planned as per protocol (Week 52, 104, or 208 or due to relapse) or an early discontinuation.

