2.8.1 Adverse events (AEs)

For all subjects enrolled in the study, AEs data will be summarized and analyzed together by treatment arms for the SAF.

Treatment emergent AEs are defined as (events started on or after the first dose of study treatment or events present prior to the first dose of study treatment but increased in severity on or after dosing based on preferred term , and within 84 days (inclusive) after the last dose of study treatment. Only primary paths within MedDRA will be considered for AE reporting.

Adverse events will be summarized by presenting, for each treatment arm, the number and percentage of subjects having any AE, having an AE in each primary system organ class and having each individual AE (preferred term).

Summaries will also be presented for AEs by severity (mild/moderate/severe) and for study treatment related AEs. If a particular AE 'severity' is missing, this variable will be listed as missing and treated as missing in summaries.

If a subject reported more than one AE with the same preferred term, the AE with the greatest severity will be presented. If a subject reported more than one AE within the same primary system organ class, the subject will be counted only once with the greatest severity at the system organ class level, where applicable.

The most common adverse events reported ($\geq z$ % in any group for each preferred term in the table by SOC and PT) will be presented in descending frequency according to its incidence in secukinumab group (combining all secukinumab treatment arms) starting from the most common event. Here threshold value z is set to 2 (%) but it may be updated following review of the dry run outputs.

Separate summaries will be provided for psoriatic arthritis, SAEs, other significant AEs leading to discontinuation from the study, and AEs leading to study treatment discontinuation.

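### Protocol 7.1 ends AE collection at the EOS visit, which contradicts the later safety contact in 5.6.1 and the SAP's 84-day window; applied literally, it leaves up to 56 of 84 post-dose days uncovered for non-serious AEs in on-schedule secukinumab patients who leave four weeks after the last dose.

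*Protocol*

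**What the plan says.** **Protocol 7.1** limits an AE to an occurrence "after providing written informed consent for participation in the study until the EOS visit". For possibly related events after the observation period it says "This information should be recorded in the investigator's source documents; however, if the AE meets the criteria of an SAE", in which case the sponsor must also be told.

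**Protocol Table 6-3, note c**: "EOS is defined as the last visit for a patient independently of whether the discontinuation or completion is planned as per protocol". The note names Weeks 52, 104 and 208, relapse and early discontinuation.

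**Protocol 5.6.1** requires a safety follow-up for all patients, by telephone for example, "30 days after the last study visit or 12 weeks after the last dose of study treatment, whichever is later". It adds: "The information to be collected at this follow-up visit includes concomitant medications, AEs, and survival status".

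**Protocol Section 6**, in the text before Table 6-1, sets a minimum: patients are to be "contacted for safety evaluations during the 30 days following the last study visit or following the last administration of study treatment". The sentence refers the reader to 5.6.1.

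**Protocol 7.2.2** requires every SAE, whatever its cause, to be reported up to 12 weeks after the last administration.

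**SAP 2.8.1** counts AEs as treatment-emergent if they occur "within 84 days (inclusive) after the last dose of study treatment". SAP 2.1.1.4 uses the same 84 days for on-treatment assessments.

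**The concern.** The 5.6.1 contact always falls after EOS, so 5.6.1 asks sites to collect events that 7.1 places outside the AE definition. The protocol does not say which section prevails. Section 7.1 is the operative AE section and names the eCRF page, whereas 5.6.1 names none. Tables 6-1 to 6-3 are presented as listing all assessments, yet none has a column for a contact after EOS. A site working from 7.1 and the tables could reasonably stop AE entry at EOS, while a site working from 5.6.1 would continue.

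The SAP's treatment-emergent tables assume the longer period. Under the 7.1 reading, how much of the 84 days is filled depends on when a patient leaves, and therefore on response and arm. A1 patients at or above PASI 50 enter follow-up, and their first scheduled visit there comes after the window has closed. A1 patients below PASI 50, and all patients in Arm C, leave earlier. Crude incidence would then compare patients watched for different lengths of time after the last dose.

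**Working it through.** **Inputs**

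- Day numbering: scheduled day = 7 × week + 1 (SAP Table 2-1 has Week 52 = Day 365 and Week 104 = Day 729).
- Last secukinumab dose: Week 48 in A1 and C1, Week 100 in A2 and C2 (Protocol 3.1).
- EOS at Week 52: C1, and A1 or B1 below PASI 50. EOS at Week 104: C2, and A2 below PASI 90 (Protocol 3.1).
- nb-UVB: one or two 12-week cycles with a break of at most 28 weeks, so the last session can be as late as 12 + 28 + 12 = Week 52.

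**The plan's own figure.** 12 weeks × 7 = 84 days, so 5.6.1, 7.2.2 and the SAP agree on the post-dose period. Section 7.1 is the one that differs.

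**Uncovered share if 7.1 is applied literally** = max(0, 84 − (EOS day − last-dose day)) / 84.

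| Patient | Last dose | EOS | Covered days | Uncovered days | Share |
|---|---|---|---|---|---|
| C1; A1 below PASI 50 | Day 337 (W48) | Day 365 | 28 | 56 | 67% |
| Same, Week 48 dose missed | Day 309 (W44) | Day 365 | 56 | 28 | 33% |
| C2; A2 below PASI 90 | Day 701 (W100) | Day 729 | 28 | 56 | 67% |
| B1, last session W52 | Day 365 | Day 365 | 0 | 84 | 100% |
| B1, last session W48 | Day 337 | Day 365 | 28 | 56 | 67% |
| B1, last session W44 | Day 309 | Day 365 | 56 | 28 | 33% |
| B1, last session W40 or earlier | Day 281 or earlier | Day 365 | 84 | 0 | 0% |
| A1 followed to W104 | Day 337 | Day 729 | 84 | 0 | 0% |

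A B1 patient treated to Week 52 has a window ending on Day 365 + 84 = Day 449 (Week 64), so B1 patients followed to Week 104 also have no gap.

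**Visit timing.** With a last dose on Day 337, an EOS visit on Day 407 (the upper limit of the SAP's Week 52 window for A1 and B1) leaves 84 − 70 = 14 days uncovered (17%). On Day 421 (the upper limit for C1) it leaves none.

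**If 5.6.1 governs instead.** The contact falls at max(last visit + 30, last dose + 84).

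- A1 and C1: max(395, 421) = Day 421.
- A2 and C2: max(759, 785) = Day 785.
- B1 treated to Week 52: max(395, 449) = Day 449.

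In each case the whole 84 days is covered.

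**Effect on time at risk.** SAP 2.4.1 ends secukinumab exposure at the last visit if that is before last dose + 84 days. With first dose on Day 1, exposure is 365 days if EOS is the last visit and 421 days if the 5.6.1 contact is. If the contact counts but the site stopped AE entry at EOS, 56 / 421 = 13% of the patient's exposure carries no non-serious AE collection. The SAP does not say which applies. For nb-UVB, 2.4.1 gives last dose + 84 days with no last-visit limit, although 2.1.1.4 states a general one.

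**How many patients.** Arm C has 24 planned patients (12 + 12), all with EOS four weeks after the last dose if they complete on schedule. The documents give no PASI 50 rate for A1. Under the planning assumption of 70% PASI 90 responders and no dropout, at most 80 × 0.30 = 24 A1 patients could be below PASI 50, so the range is 0 to 24.

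**The case against.** The strongest reply is that nothing is lost under the plan as a whole. Section 5.6.1 applies to all patients, lists AEs among the data and matches the SAP's 84 days. No passage says that the AE page closes at EOS. The source-document sentence in 7.1 concerns events after an observation period that the protocol does not define. This stands in part: the gap is conditional on a site following 7.1 over 5.6.1. It does not remove the contradiction, because 7.1 is where AEs are defined.

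A reader might infer four stronger things that the documents do not support.

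- *Every patient with EOS at Week 52 loses two thirds of the window.* That figure holds for on-schedule secukinumab patients. For B1 the share depends on the last session, and A1 and B1 patients stopping at Week 104 have no gap.
- *Section 6 sets a third, 30-day cut-off.* Its sentence is worded as a minimum and refers to 5.6.1. It is loosely aligned, not a rival end date.
- *Serious events are missed.* An SAE is defined in 7.2.1 as a kind of AE, so a literal 7.1 sits badly with 7.2.2 too. But 7.2.2 is explicit, and SAEs are covered to 12 weeks.
- *All safety rates are distorted.* SAP 5.2.1 censors exposure-adjusted incidence at the end of observation or last dose + 84 days, whichever is earlier. Unequal observation is therefore handled in those denominators, provided that the end of observation is the date when AE collection stopped.

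The setting also limits the consequence. Arm C belongs to the Mechanistic Sub-study, which has no formal testing. Patients who stop treatment early are meant to return for scheduled assessments before EOS (5.6.2), so early leavers cannot be given one figure. A telephone contact has no laboratory test in its listed content, so it would not detect a silent neutropenia under either reading.

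**Conclusion.** The contradiction between Protocol 7.1 and Protocol 5.6.1, Protocol 7.2.2 and the SAP is real and should be resolved. Its size is conditional. If 7.1 is applied literally, 56 of 84 post-dose days (67%) are uncovered for non-serious AEs in on-schedule secukinumab patients with EOS four weeks after the last dose. The share is 0% to 100% for B1 patients with EOS at Week 52, and nil for A1 and B1 patients followed to Week 104 or beyond. The consequence is mainly for crude incidence of non-serious treatment-emergent AEs, whose capture would vary with response, arm and site practice. These figures assume doses and visits on nominal days. The documents do not show which section sites followed, so they do not establish that any event went unrecorded.

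**What to change.** - **Protocol 7.1:** end the AE period at the safety follow-up contact of Section 5.6.1 instead of at the EOS visit, and state that AEs reported at that contact go on the Adverse Event eCRF page. The contact is never earlier than 12 weeks after the last dose, so collection then covers the SAP window for every patient who is reached. Where it falls later, the SAP's 84-day rule still decides what is treatment-emergent.
- **Protocol Section 6:** align the 30-day minimum sentence with 5.6.1.
- **SAP 2.1.1.4, 2.4.1 and 5.2.1:** state whether the 5.6.1 contact counts as the last visit when exposure and time at risk are cut, and apply one rule to both treatments.

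The cost is wording and a small amount of data entry, since the contact is already required. SAP 2.14.2 records study termination at 30 June 2023, so a protocol change may come too late to alter collection. In that case the SAP or study report should say which end of AE collection sites applied, and whether AEs reported at the 5.6.1 contact reached the database.
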